# 2. STUDY OBJECTIVES AND ENDPOINTS

Objectives	Endpoints
Primary	

 
• Evaluate safety and tolerability of BION-1301 when administered as a single-agent
 
	
 
• Incidence of dose-limiting toxicities (DLTs), treatment-emergent adverse events (TEAEs), and changes in safety parameters
 

Secondary	

 
• Characterize the pharmacokinetic (PK) and pharmacodynamic (PD) profile of BION-1301
 
• Evaluate clinical activity of BION-1301
 
	
 
• PK parameters based on BION-1301 serum levels following a single dose and after repeated dosing *
 
• Change from baseline in soluble anti-proliferation-inducing ligand (APRIL)*
 
• Relative reduction in serum and urine monoclonal protein (M-protein) levels defined as the maximum percent reduction from baseline
 

\* pharmacokinetic, biomarker, and pharmacodynamic endpoints will be addressed in a separate standalone PK/PD analysis plan

### 3. STUDY DESIGN

#### 3.1. Study Design and Population

ADU-CL-16 is an open-label, multicenter, first in human, dose escalation study to evaluate the safety, tolerability, and PK-PD of BION-1301, a first-in-class monoclonal antibody targeting APRIL. The population for this study consists of adults with relapsed or refractory Multiple Myeloma (MM) whose disease has progressed after at least 3 prior systemic therapies. BION-1301 will be administered in 28-day cycles.

The study was planned to be conducted in 2 parts as depicted below. Phase 1 was conducted using a 3+3 dose escalation design and sought to determine the Recommended Phase 2 Dose (RP2D) by evaluating safety and tolerability and characterizing the PK-PD of BION-1301. Dose escalation decisions were based on available safety, PK-PD, and efficacy data from all evaluable subjects in each cohort.

The dosing interval was once every 2 weeks (Q2W) during initial dose escalation. Additional cohorts were enrolled to evaluate weekly (QW) dosing for up to 8 weeks, followed by Q2W dosing with the same or a lower dose. PK-PD data were evaluated for each cohort to inform the dosing schedule to be evaluated in subsequent cohorts. Subjects continued dosing until disease progression or unacceptable toxicity.

Once an RP2D and dosing schedule was identified, Phase 2 of the study was planned to open and continue to evaluate the safety and preliminary efficacy of BION-1301 administered as a single agent or with low-dose dexamethasone.

[figure not shown]
Additional guidelines specific to Phases 1 and 2 of the study as well as a schedule of visits and procedures are provided in the study protocol.

The study was prematurely terminated by the Sponsor on 07 May 2019 after enrollment of 21 subjects into 6 cohorts in Phase 1 of the study. Only the objectives and endpoints specified in the protocol for Phase 1 and identified in section 2 above will be described in this ASAP.

Figure 1: Study Design

Screening Period Confirm eligibility Up to 28 days	Treatment Period (28-day Dosing Cycles) Until disease progression or unacceptable toxicity BION-1301 (IV infusion) +/- Dexamethasone (40 mg QW PO; Phase 2 only)	Follow-Up Period (Q12W) Safety reporting Subsequent cancer treatment Survival
--	---	---

**Study Population & Enrollment Plan:**

### 3.2. Randomization and Blinding

All subjects were sequentially assigned a unique identification number during Screening.

Subjects meeting all inclusion and exclusion criteria and completing all screening requirements were assigned treatment depending on the study enrollment status:

- In Phase 1 of the study, subjects were sequentially assigned to dose cohorts as specified in the study design
- The Cycle 1 Day 1 dose was staggered by at least 24 hours for the first 2 subjects dosed in each cohort

All study treatments were administered open-label; no study participants or site personnel were blinded to study treatment.

### 3.3. Sample Size Considerations

During Phase 1, dose escalation was based on 3+3 guidelines to determine the RP2D and evaluate safety data (including DLTs and TEAEs) and assess the PK-PD of each dose level. The sample size in Phase 1 is predicated on the number of dosing cohorts examined and the number of observed DLTs.

### 3.4. Data Monitoring Committee/Safety Review Team

There was no formal Data Monitoring Committee for this study. Safety data and all unacceptable toxicities were reviewed by the Safety Review Team (SRT) comprised of participating Investigators in the study, the Medical Monitor, and representatives of the Sponsor. Dose escalation and reduction decisions, additional enrollment specifications, and recommendation of the RP2D(s) and dosing schedule for expansion were planned to be made by the SRT. TEAEs, DLTs and safety data will continue to be reviewed by the SRT throughout the study.

### 3.5. Interim Analysis

A Safety Review Team monitored data during the study, as described in Section 3.4. Otherwise, no other formal interim analysis activities were planned per the protocol.

### 3.6. Timing of Analyses

All available phase 1 data were reviewed to enable dose-escalation and dose selection decisions and will be part of the final analysis as of the final database lock. As of 07 May 2019, Aduro decided to cease development activities for BION-1301 after the last subject in cohort 6 completed treatment. The Phase 2 portion of the study was not enrolled.

## 4. DATA ANALYSIS CONSIDERATIONS

All analyses will be conducted based on SAS 9.4 or higher.

All clinical data in the database, with the exception of laboratory accession numbers, central lab collection dates, and study drug supply administrative data, will be presented in by-subject data listings.

Unless otherwise stated, all listings will be sorted by cohort, site ID, subject number, and assessment date (and time, if available).

Unless stated otherwise, continuous data will be summarized based on n, mean, median, standard deviation (SD), first quartile (Q1), third quartile (Q3), minimum value, and maximum value. For continuous variables, if n=1, the SD cannot be calculated and will be displayed as Not applicable (NA).

Unless stated otherwise, categorical data will be summarized using n and percentage based on the number of non-missing values.

- The number of missing values will be presented as a separate category with no percentage, but only if one or more subjects are missing data.

Sponsor: Aduro Biotech, Inc.  
Protocol Number: ADU-CL-16  
Version and Date: Version 1.0, 18JUL2019

- Counts of zero will be presented without percentages.

#### Precision

- Mean, Median, Q1, and Q3: one additional decimal place to that reported for Minimum and Maximum
- SD: two additional decimal places than the Minimum and Maximum
- Percentages: reported to one decimal place

Descriptive summaries will be presented by cohort and overall. No statistical significance test will be performed.

All data up to the time of study completion/withdrawal from the study will be included in the analysis, regardless of duration of treatment.

With exception to missing data handling noted in section 5.10, data will not be imputed for analysis purposes.

Summaries by visit will be produced for sample sizes  $\geq 2$ .

Numbering for data displays will be based on ICH E3.

#### 4.1. Stratification and Covariates

There are no formal plans for analysis stratification.

#### 4.2. Evaluation of Subgroups

Subgroup analyses are not planned to be performed for the final analysis.

#### 4.3. Multiple Comparisons and Multiplicity

Not Applicable.

### 5. GENERAL DATA HANDLING CONVENTIONS

#### 5.1. Assigned and Actual Treatment

Subjects were assigned to a study treatment based on study design as seen in Figure 1 and detailed in Table 1 and Table 2. The Phase 1 portion of the study evaluated single-agent BION-

1301, open-label, where subjects received infusion(s) at the study site. Subjects will be displayed based on assigned study dosing schedule.

Table 1: Phase 1 – BION-1301 Enrollment and Dose Escalation Plan

BION-1301 Dose Cohort (proposed dose )	0/3 subjects have DLT	1/3 subjects have DLT	≤1/6 subjects have DLT	≥2 in a cohort have DLT
1 (50 mg) Q2W	Escalate to Dose Cohort 2 per Dose Escalation rules	Expand to 6 evaluable subjects	Escalate to Dose Cohort 2 per Dose Escalation rules	MTD exceeded; de-escalate to Dose Cohort -1 
2 (150 mg) Q2W	Escalate to Dose Cohort 3 per Dose Escalation rules	Expand to 6 evaluable subjects	Escalate to Dose Cohort 3 per Dose Escalation rules	MTD exceeded; no further enrollment at dose level
3 (450 mg) Q2W	Escalate to Dose Cohort 4 per Dose Escalation rules	Expand to 6 evaluable subjects	Escalate to Dose Cohort 4 per Dose Escalation rules	MTD exceeded; no further enrollment at dose level
4 (1350 mg) Q2W	Escalate to Dose Cohort 5 per Dose Escalation rules	Expand to 6 evaluable subjects	Escalate to Dose Cohort 5 per Dose Escalation rules	MTD exceeded; no further enrollment at dose level
5 (2700 mg)  Q2W	Expand to 6 evaluable subjects	Expand to 6 evaluable subjects	Maximum dose reached	MTD exceeded; no further enrollment at dose level
6 (1350 mg)  QW (x8) -> Q2W	Expand to 6 evaluable subjects	Expand to 6 evaluable subjects	Maximum dose reached	MTD exceeded; no further enrollment at dose level

 
Dose levels may be escalated up to maximum 3-fold increases; actual dose determined empirically by SRT based on available safety, PK-PD, and efficacy data. Additional incremental dose levels (either increased or decreased) may be investigated.
 
DLT evaluation period is 28 days after first dose of BION-1301 (Cycle 1).
 
If a 4th subject is enrolled, all 4 subjects must complete DLT evaluation period. If 1/4 subjects has DLT, expand to 6 evaluable subjects.
 
SRT will evaluate all available data and decide whether to initiate Dose Cohort -1 at a dose of 5 mg.
 
Evaluation of additional intermediate dose cohorts will follow the same 3+3 rules for dose cohort expansion. Dose level will not exceed 2700 mg.
 
Dosed every week for 8 weeks, followed by every 2 week dosing (see Table 2)
 
 DLT = dose-limiting toxicity; MTD = maximum tolerated dose; SRT = safety review team; Q2W = dosed every 2 weeks; QW = dosed every week				

Table 2: Phase 1 - BION-1301 Dosing Schedule Exploration Options (21-day cycles)

BION-1301 Dose Schedule	QW Dosing (Assigned QW dose level)	Q2W Dosing (Assigned dose level)
Q2W	N/A	All Cycles: Days 1, 15
QW × 8 → Q2W	Cycle 1: Days 1, 8, 15, 22 Cycle 2: Days 1, 8, 15, 22	Cycle 3 and beyond: Days 1, 15

 QW and Q2W assigned dose level may vary within a given schedule; the BION-1301 dose administered during Q2W dosing may be at the same dose level used for QW dosing, or at a lower dose level.

 Doses given on Q2W dosing schedule are always on Days 1 and 15 of each cycle; one week following the last QW dose

## 5.2. Reference Dates

- Informed Consent date is defined as the eCRF provided date on which a subject signed the informed consent.
- Treatment start date is defined as the date of first dose of study drug.
- Treatment end date is defined as the date of last dose of study drug.
- Age will not be calculated and will come directly from the eCRF. The eCRF uses the informed consent date as its reference date for age calculation.
- Safety data, such as AEs and laboratory assessments will use the treatment start date as a reference date.
- Study day will be based on treatment start date as a reference date.

## 5.3. Study Day and Duration Variables

Reference date calculations will generally be defined as the following, assuming non-missing dates:

- date of interest – reference date + 1 when the date of interest >= reference date;
- otherwise, date of interest – reference date.

If either date is missing, reference date calculations will not be performed. Date imputation will be performed as identified in Section 5.6.

For instance, study day will be based on the treatment start date as the reference date and would either have a negative value if collected before dosing or a positive value if collected on or after the day of drug dosing; there will be no study day zero.

Duration of time is dependent on reference dates and will be calculated in a manner similar to that of the reference date calculation, assuming that dates of interest will strictly follow reference dates (e.g. no negative values). For example, duration on study is defined as the end of study date – treatment start date + 1. Duration of treatment is defined as treatment end date – treatment start date + 1, where treatment end date is the date of last dose of study drug. Subjects still receiving ongoing treatment or participating in study follow up at the time of analysis will use imputed treatment end and end of study dates as described in Section 5.7.

When reporting duration outcomes, the results (in days) above will be converted to an appropriate unit. When reporting in months it will be divided by 30.4375; for reporting in weeks it will be divided by 7; and for reporting in years it will be divided by 365.25.

#### 5.4. Study Time Periods

Safety reporting in general will be classified by the following study periods for analysis:

- Pre-therapy is defined as the period prior to a subject’s treatment start date.
- On-therapy is defined as the period between a subject’s treatment start date and treatment end date +28 days.
- Post-therapy is defined as the period of time following the on-therapy period.

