Prior/Concomitant Medications	X	X	X	X	X	X	X	X	X	X	X	X	X	X	X	X	
Laboratory Specimens (obtain prior to dosing, unless otherwise specified)																	
Virology Screen, β-2M, CRP ¹²	X																
Hematology, Chemistry ¹²	X	X ¹²	X		X	X	X	X	X	X	X	X	X	X	X	X	
Coagulation ¹²		X ¹²				X											
Urinalysis ¹²	X	X ¹²						X					X		X		
Pregnancy Test (WOCBP) ¹²	X	X						X					X		X		
Immunogenicity (serum) ^{13, 14}		X				X		X			X		X ¹⁴		X		
BION-1301 PK (serum) ^{13,15, 16}		X ¹⁵	X	X	X	X ¹⁵	X ¹⁵	X ¹⁵		X	X ¹⁵	X ¹⁵	X ¹⁶		X		
PD Biomarkers (blood,serum) ^{13,15,16}	X ¹³	X ¹⁵	X	X	X	X ¹⁵	X ¹⁵	X ¹⁵		X	X ¹⁵	X ¹⁵	X ¹⁶		X		
Bone Marrow Sample ^{13, 17}	X										X		As indicated ¹⁷		X		
PBMC (select sites) ¹⁸	X	X												Odd-cycles ¹⁸	X		
Study Drug Administration (assigned; see Table 2-2)																	
BION-1301 Q2W Schedule ¹⁹		X				X		X			X		X	X			
BION-1301 QW Schedule ²⁰		QW doses as assigned (Table 2-2) Q2W thereafter ²⁰											X	X			
Dexamethasone (Phase 2 only) ²¹		Self-administered in morning on Days 1, 8, 15, 22 of each cycle (prior to BION-1301 dose)															

FOOTNOTES FOR Table 2-1 (See [Section 7.5](#) for additional information)

- ¹ Cycle length is 28 days.
- ² Cycle 1 Day 3 Visit: Subjects will complete Day 3 visit during Cycle 1; based on available PK-PD data, visit may be moved out to Day 5 if needed for complete assessment of PK-PD profile. Sponsor will notify sites of any change in visit schedule.
- ³ EOT Visit occurs within 28 days (+7 days) after the last dose of study drug or prior to commencing new therapy. If EOT occurs earlier, schedule a telephone contact at least 28 days post-last dose of study drug to satisfy reporting requirements for AEs. If an AE requires monitoring beyond the EOT Visit, follow until resolution or confirmed stability of the event.
- ⁴ Follow-up: Subjects may be contacted via phone for survival and any subsequent cancer-related therapies. A telephone contact should also be scheduled for 90 days post-last dose of study drug to satisfy reporting requirements for SAEs.
- ⁵ Medical History, Height: includes demographic data (date of birth, age, gender, ethnicity, and race). Medical history includes all active conditions and any condition considered to be clinically significant by the Investigator. Record details of MM date of diagnosis, primary tumor histology, prior surgery(ies), radiation therapy, chemo- and biological therapies, and stage of cancer. Obtain standing height.

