7.5 Study Assessments and Procedures

Screening assessments will be conducted to confirm eligibility and to obtain baseline measurements. Screening must be completed within 28 days prior to first dose of study drug. An enrollment form will confirm subject eligibility after completion of all screening procedures. Subjects must initiate dosing of study drug within 2 weeks from the date of the approved enrollment form.

Subjects will be requested to complete multiple clinic visits during the initial two dosing cycles; visit frequency is reduced beginning at Cycle 3 and beyond. An EOT Visit will occur 28 days after the last dose of study drug. If the subject begins another anticancer therapy before the end of the 28-day period, all EOT Visit assessments should be completed prior to commencing the new therapy. Unresolved AEs will be monitored until resolution or confirmed stability of the event.

Subjects who discontinue study treatment for reasons other than progressive disease should continue tumor response assessments as per the standard of care frequency until disease progression is documented, withdrawal of consent, or study end.

Follow-up calls will occur every 12 weeks after the last dose of study drug. Data will be collected on survival and any subsequent cancer-related therapies. Telephone contact(s) should also be scheduled to satisfy safety reporting requirements as specified in [Table 7-4](#).

All study visits (and visit windows), assessments, and procedures will be performed as indicated in the Schedule of Events ([Table 2-1](#)). On days when study drug is administered, assessments should be performed prior to dosing unless otherwise specified. Further details of study procedures and assessments can be found in the Study Reference and Laboratory Manuals.

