7.5.4.2 Safety Laboratory Assessments

Routine hematology, serum chemistry, and urinalysis will be conducted to assess eligibility and as a measure of safety per protocol requirements. All clinical laboratory evaluations will be performed by the institution's local laboratory. Testing may be completed up to five days prior to each study drug administration. Fasting is not required.

The following routine laboratory parameters will be evaluated at Screening through EOT as indicated:

- Hematology: complete blood count (white blood cells, red blood cells, hematocrit, hemoglobin, platelet count, and differential)
- Serum chemistry: sodium, potassium, chloride, bicarbonate, glucose, blood urea nitrogen, creatinine, lactate dehydrogenase, alanine aminotransferase (ALT), aspartate aminotransferase (AST), alkaline phosphatase, bilirubin (total, direct, indirect), total protein, albumin, calcium, magnesium, uric acid, and phosphate
- Coagulation panel: D-dimer, fibrinogen, INR of PT, and aPTT
- Urinalysis (dipstick): bilirubin, blood, glucose, ketones, leukocytes, nitrite, pH, protein, and specific gravity

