7.6.6 Safety Analyses

AEs will be coded according to the current Medical Dictionary for Regulatory Activities (MedDRA) and assessed for severity by the Investigator using the National Cancer Institute Common Terminology Criteria for Adverse Events (NCI-CTCAE) v. 4.03. TEAEs will be summarized by system organ class and preferred term and presented in decreasing order of frequency. Incidences of TEAEs and SAEs will be summarized overall and with respect to CTCAE grade and relationship to study drug. TEAEs leading to study drug discontinuation, dose reduction/interruption, and with an outcome of death will also be summarized. Incidence SAEs will be summarized overall and with respect to study drug.

Shifts from baseline in ECOG and changes in vital signs, ECG parameters, hematology and serum chemistry parameters from baseline to the EOT will be examined. Treatment-emergent changes from normal to abnormal values in key laboratory parameters will be identified. Changes in NCI toxicity grading will be presented using shift tables and listings of clinically significant values.

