## 5.5. Baseline, Post-Baseline Changes, and Last Observed Value (LOV)

Unless stated otherwise, baseline and post-baseline change values will be based on the following:

Baseline will be based on the last non-missing value collected prior to or on the treatment start date [and time, if applicable]. Post-baseline values will be those collected after the treatment start date.

Change from baseline is defined as: value at visit – baseline value.

Percentage change from baseline is defined as: (value at visit – baseline value)/baseline value X 100%.

Most extreme change: The maximum most extreme change will be based on be the maximum grade change. This calculation will consider assessments collected during the on-therapy period and assessed with CTCAE grading, scheduled or unscheduled.

Maximum percent reduction is defined as the largest percent reduction in the change from baseline at any visit.

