## **9.2. Clinical Laboratory Evaluations**

Clinical chemistry and hematology parameters will be reported based on the International System of Units (SI). The following laboratory evaluations will be reported in data summaries, with asterisks (\*) indicating those that will be graded using NCI-CTCAE:

Hematology: Hematocrit, white blood cell\*, absolute neutrophil count\*, lymphocytes\*, hemoglobin\*, monocytes, eosinophils, basophils, red blood cell, and platelet count\*

Clinical chemistry: sodium\*, potassium\*, chloride, bicarbonate, glucose\*, blood urea nitrogen, creatinine\*, lactate dehydrogenase, alanine aminotransferase\*, aspartate aminotransferase\*,

Sponsor: Aduro Biotech, Inc.  
Protocol Number: ADU-CL-16  
Version and Date: Version 1.0, 18JUL2019

alkaline phosphatase\*, bilirubin (total\*, direct, indirect), total protein, albumin\*, calcium, magnesium\*, phosphate\*, and uric acid.

Safety laboratory assessments will be summarized by absolute value and change from baseline at each visit will be displayed by cohort and cycle.

Shift tables displaying the shift from baseline to the worst value of NCI-CTCAE grade will be presented based on the most extreme change as it relates to the relevant NCI-CTCAE definition.

All laboratory parameters will be provided in subject data listings.

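### The worst-grade laboratory shift tables stop at last dose + 28 days, so an EOT panel drawn in the permitted +7 day tolerance (days 29 to 35) cannot enter them

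*SAP*

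**What the plan says.** **SAP.** Section 5.4 places the on-therapy period between the "treatment start date and treatment end date +28 days". Section 5.2 fixes the anchor: "Treatment end date is defined as the date of last dose of study drug". Section 5.5 defines the most extreme change and restricts its data: "This calculation will consider assessments collected during the on-therapy period and assessed with CTCAE grading, scheduled or unscheduled". Section 9.2 then uses it: "Shift tables displaying the shift from baseline to the worst value of NCI-CTCAE grade will be presented based on the most extreme change". Section 5.4.1 runs events of special interest to the EOT visit rather than to a fixed number of days. Section 10, which records changes to the planned analysis, mentions no shortened laboratory period.

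**Protocol.** Table 2-1, footnote 3, gives the visit window: "EOT Visit occurs within 28 days (+7 days) after the last dose of study drug or prior to commencing new therapy". Section 7.5 gives the target: "An EOT Visit will occur 28 days after the last dose of study drug". Section 7.5.4.2 has the safety laboratory panels taken up to that visit: "The following routine laboratory parameters will be evaluated at Screening through EOT as indicated". Section 7.6.6 states the span of the laboratory analysis: "hematology and serum chemistry parameters from baseline to the EOT will be examined". It adds, in a separate sentence, that changes in toxicity grade will be shown in shift tables.

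**The concern.** The analysis period closes on the very day the EOT visit is due, and the visit's tolerance opens only after that day. A site that follows the protocol and sees the subject on day 31 supplies a panel that the SAP classes as post-therapy. Its grades then have no route into the shift table.

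Changes in safety parameters belong to the primary endpoint in SAP section 2. The worst-grade shift table is the summary that shows how far each subject's laboratory grade deteriorated. Leaving out an assessment can lower a subject's recorded worst grade or leave it unchanged; it cannot raise it. Any error therefore makes the laboratory safety profile look better.

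The SAP also treats related laboratory data in two ways. Protocol 8.1.3 defines the event of special interest by Hy's Law laboratory values, and SAP 5.4.1 counts it through the EOT visit. A qualifying result on day 32 would fall within that reporting period, yet its transaminase and bilirubin grades would be missing from the shift tables.

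**Working it through.** The plan states no figure for this point, so there is none to reproduce. The check compares dates, counted in days after the last dose (last dose = day 0).

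**Inputs**
- On-therapy end: day 28 (SAP 5.4, with the anchor in 5.2).
- EOT target: day 28 (Protocol 7.5 and Table 2-1).
- EOT tolerance: +7 days (Protocol Table 2-1 and footnote 3).
- Enrolment: 21 subjects in 6 cohorts (SAP 3.1). Cohort sizes are not given.

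**Step 1: latest compliant EOT visit.** 28 + 7 = day 35.

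**Step 2: compliant days outside the on-therapy period.** Days 29 to 35, which is 35 − 28 = 7 days. Day 28 itself and any earlier EOT visit are inside.

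**Step 3: does another SAP rule bring those days back?** Section 5.7 works by nominal visit without date windowing and allows unscheduled data into most-extreme summaries. Section 4 says in general terms that data up to study completion or withdrawal are included. Neither removes the specific restriction in 5.5, which covers scheduled and unscheduled assessments alike. Read as written, the restriction governs the shift table.

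**Step 4: when does a cell change?** Let G be the worst on-therapy grade for a subject and analyte up to day 28, and E the EOT grade on days 29 to 35. The table shows G; with the EOT panel included it would show max(G, E). The two differ only if E > G.

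**Step 5: size of one changed subject.** In a cohort of 3, 1/3 = 33 percentage points. In a cohort of 6, 1/6 = 17 percentage points. These sizes are assumptions taken from the 3+3 plan.

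**Step 6: how many panels could be late?** The documents do not say. If a share p of 21 subjects had the EOT visit on days 29 to 35, the expected number is 21p and, with independent subjects, the chance of at least one is 1 − (1 − p)^21.

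| Assumed p | Expected late panels | Chance of at least one |
|---|---|---|
| 10% | 2.1 | 0.89 |
| 25% | 5.25 | 0.998 |
| 50% | 10.5 | > 0.999 |

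These are counts of late panels, not of changed cells. Changed cells also need E > G, for which there is no figure.

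**Step 7: after the fix.** If the laboratory period runs to the EOT visit, up to day 35, none of days 29 to 35 is excluded.

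**The case against.** The strongest reply is that the data are missing from one display, not from the analysis. SAP 9.2 summarises values and changes at each visit, and 5.7 does so by nominal visit, so a day-32 EOT result appears there and in the listings. This stands and limits the reach. It does not dispose of the point, because by-visit summaries of values and changes do not show the worst grade.

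A second reply is that last dose + 28 days is the protocol's own window for treatment-emergent adverse events, so using it for laboratory data is a reasonable alignment. It is also true that the baseline-to-EOT sentence in Protocol 7.6.6 is separate from the shift-table sentence, which names no end date. The alignment could be defended if it were declared. SAP section 10 does not declare it, and SAP 5.4.1 departs from it for Hy's Law events.

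Third, this is a terminated Phase 1 study with an abbreviated SAP, descriptive summaries and no significance tests. No decision rule depends on these tables. That stands and holds the severity down.

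A reader might also infer more than the documents support:
- *That EOT laboratory results drop out generally, or that seven-eighths of them do.* Seven of the eight calendar days from 28 to 35 are excluded, but the target is day 28, earlier visits are permitted, and the spread of actual visit days is not reported.
- *That the EOT panel is the only scheduled panel after the final infusion.* Dosing-day panels are pre-dose, but a subject last dosed on Day 15 who attends Day 1 of the next cycle has a panel about 14 days later, inside the on-therapy period.
- *That subjects who stop for toxicity are hit hardest.* Protocol 7.5.3.7 requires clinically significant abnormal values to be followed with repeat tests, and SAP 5.5 admits unscheduled results, so these subjects may well have other panels within 28 days.

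**Conclusion.** The mismatch is real and its severity is minor. As written, the SAP excludes compliant EOT haematology and chemistry on days 29 to 35 from the worst-grade shift tables, and only from those tables. Any resulting bias is downward. Its frequency cannot be estimated from the documents, because they give neither the number of late EOT visits nor how often a late grade exceeds all earlier on-therapy grades.

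The figures of 33 and 17 percentage points describe one affected subject in a cohort of 3 or 6. They rest on assumed cohort sizes and on the late grade being that subject's worst. They are not an estimate of the overall effect. The documents do not support a claim that the laboratory safety conclusions are materially distorted.

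**What to change.** Add one sentence to SAP 5.5, cross-referenced from 9.2: for laboratory worst-grade derivations only, the period ends at the later of last dose + 28 days and the nominal EOT visit, up to last dose + 35 days. Leave the adverse event window as it is.

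The cost is that sentence and a changed date cut in the shift-table program. No new data are needed. Effects of later treatment are unlikely to enter, because Protocol 7.5 requires EOT assessments before any new anticancer therapy and 7.4.7 keeps such therapy prohibited until the EOT visit is complete.

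There are two downsides. The laboratory window becomes up to 7 days longer than the window for non-serious treatment-emergent events, so a day-33 grade could appear in the shift table without a matching treatment-emergent event; a table footnote should say so. Some cells may also look slightly less favourable.

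If the sponsor prefers to keep the 28-day cut, the minimum is to record it in SAP section 10 as a departure from the baseline-to-EOT span and to footnote the shift tables accordingly.
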